## **2.5 Rationale for this study**

With over 25 AEDs approved (15 in the last 15 years), the majority of patients with epilepsy and focal-onset or focal to bilateral tonic-clonic (previously called "secondary generalized") seizures have options for effective monotherapy and/or combination therapies early in the treatment paradigm; however, none of the options differentiate by superior efficacy. Seizure control has only changed marginally even with the latest new AED treatments (Brodie et al, 2012) and for the majority of severely affected and drug-resistant patients, there are few, if any, treatment options remaining.

Padsevonil is an AED with a dual mechanism of action, specifically synthesized and designed for increased anticonvulsant activity and hence for the treatment of seizures in patients with epilepsies resistant to currently available drug therapies. Based on the evidence of superior seizure control compared with other marketed AEDs across several preclinical models of epilepsy and the results of the proof of concept study, EP0069, treatment with PSL has the potential to benefit an underserved epilepsy population with high unmet medical need, namely

those who have drug-resistant epilepsy whose uncontrolled focal-onset seizures constitute a substantial threat to their health and well-being. The current study, EP0092, will evaluate the efficacy and safety of 3 dose regimens of PSL administered concomitantly with up to 3 AEDs compared with placebo for treatment of observable focal-onset seizures in subjects with drug-resistant epilepsy.

### **3 STUDY OBJECTIVES**

#### **3.1 Primary objective**

The primary objective is to evaluate the efficacy of the 3 selected dose regimens of PSL administered concomitantly with up to 3 AEDs compared with placebo for treatment of observable focal-onset seizures in subjects with drug-resistant epilepsy.

#### **3.2 Secondary objective**

The secondary objective is to assess the safety and tolerability of PSL in relation to placebo.

#### **3.3 Other objectives**

##### **3.3.1 Efficacy objectives**

The other efficacy objective is to assess HRU and quality of life.

##### **3.3.2 Pharmacokinetic objectives**

The PK objectives are to:

- Evaluate the steady-state PK of PSL
- Evaluate the impact of enzyme-inducing concomitant AEDs on PSL exposure
- Evaluate concomitant AED (and/or relevant metabolites) plasma levels

### **4 STUDY VARIABLES**

#### **4.1 Efficacy variables**

Seizure frequency refers to 28-day adjusted frequency. Observable focal-onset seizures refer to focal aware (Type IA1), focal unaware (Type IB), and focal to bilateral tonic-clonic (Type IC) seizures (ILAE Classification of Epileptic Seizures, 1981). Focal-onset seizures include all Type I seizures. Seizure-free status and seizure-free days include all (Types I, II, and III) seizure types.

##### **4.1.1 Primary efficacy variable**

###### **4.1.1.1 Primary efficacy variable for the US FDA, PMDA, Chinese FDA, and other regulatory authorities not specified in Section 4.1.1.2**

The primary efficacy variable is the change in log-transformed observable focal-onset seizure frequency from Baseline, over the 12-week Maintenance Period.

#### **4.1.1.2 Primary efficacy variable for EMA and regulatory authorities who reference EMA**

The primary efficacy variable is the 75% responder rate, where a responder is a subject experiencing a  $\geq 75\%$  reduction in observable focal-onset seizure frequency from Baseline, over the 12-week Maintenance Period.

#### **4.1.2 Secondary efficacy variables**

##### **4.1.2.1 Secondary efficacy variables for the US FDA, PMDA, Chinese FDA, and other regulatory authorities not specified in Section 4.1.2.2**

The secondary efficacy variables are as follows:

- The 75% responder rate, where a responder is a subject experiencing a  $\geq 75\%$  reduction in observable focal-onset seizure frequency from Baseline, over the 12-week Maintenance Period
- The 50% responder rate, where a responder is a subject experiencing a  $\geq 50\%$  reduction in observable focal-onset seizure frequency from Baseline, over the 12-week Maintenance Period
- Percent reduction in observable focal-onset seizure frequency from Baseline, over the 12-week Maintenance Period

##### **4.1.2.2 Secondary efficacy variables for EMA and regulatory authorities who reference EMA**

The secondary efficacy variables are as follows:

- The change in log-transformed observable focal-onset seizure frequency from Baseline, over the 12-week Maintenance Period
- The 50% responder rate, where a responder is a subject experiencing a  $\geq 50\%$  reduction in observable focal-onset seizure frequency from Baseline, over the 12-week Maintenance Period
- Percent reduction in observable focal-onset seizure frequency from Baseline, over the 12-week Maintenance Period

#### **4.1.3 Other efficacy variables (this list applies for all regulatory authorities)**

The other efficacy variables are as follows:

- Change from Baseline in log-transformed observable focal-onset seizure frequency over the first 4 weeks, second 4 weeks, and third 4 weeks of the 12-week Maintenance Period
- Change from Baseline in log-transformed observable focal-onset seizure frequency over the 16-week Treatment Period
- The 50% responder rate, where a responder is a subject experiencing a  $\geq 50\%$  reduction in observable focal-onset seizure frequency from Baseline, over the 16-week Treatment Period

- The 75% responder rate, where a responder is a subject experiencing a  $\geq 75\%$  reduction in observable focal-onset seizure frequency from Baseline, over the 16-week Treatment Period
- The 90% responder rate, where a responder is a subject experiencing a  $\geq 90\%$  reduction in observable focal-onset seizure frequency from Baseline, over the 12-week Maintenance Period
- Percent reduction in observable focal-onset seizure frequency from Baseline, over the 16-week Treatment Period
- Change from Baseline in log-transformed focal-onset (Type I) seizure frequency over the 12-week Maintenance Period
- The 50% responder rate, where a responder is a subject experiencing a  $\geq 50\%$  reduction in focal-onset (Type I) seizure frequency from Baseline, over the 12-week Maintenance Period
- The 75% responder rate, where a responder is a subject experiencing a  $\geq 75\%$  reduction in focal-onset (Type I) seizure frequency from Baseline, over the 12-week Maintenance Period
- The 90% responder rate, where a responder is a subject experiencing a  $\geq 90\%$  reduction in focal-onset (Type I) seizure frequency from Baseline, over the 12-week Maintenance Period
- Percent reduction in focal-onset (Type I) seizure frequency from Baseline, over the 12-week Maintenance Period and the 16-week Treatment Period
- Seizure-freedom status (“Yes”/“No”) during the 12-week Maintenance Period and the 16-week Treatment Period
- Number of seizure-free days during the 12-week Maintenance Period and the 16-week Treatment Period
- Cumulative responder rate during the 16-week Treatment Period
- Change in the Seizure Severity Global Item (SSG) scores from Baseline to Week 4 during the Maintenance Period (Visit 4) and the end of the 16-week Treatment Period (Visit 7)
- Change in Quality of Life Inventory in Epilepsy-31-P (QOLIE-31-P) scores from Baseline to Week 4 during the Maintenance Period (Visit 4) and the end of the 16-week Treatment Period (Visit 7)
- Change in HADS scores from Baseline to Week 4 during the Maintenance Period (Visit 4) and to the end of the 16-week Treatment Period (Visit 7)
- Time to return to Baseline observable focal-onset seizure frequency during the 12-week Maintenance Period
- Use of health-related outcomes and HRU, including healthcare provider consultations not foreseen by protocol, caregiver support, concurrent medical procedures, concomitant medications, and hospitalizations

## **4.2 Safety variables**

### **4.2.1 Primary safety variables**

The safety variables are as follows:

- Incidence of TEAEs reported by the subject and/or caregiver or observed by the Investigator during the entire study
- Incidence of TEAEs leading to study withdrawal
- Incidence of treatment-emergent serious adverse events (SAEs) during the entire study

### **4.2.2 Other safety variables**

Other safety variables are as follows:

- Incidence of TEAEs reported by the subject and/or caregiver or observed by the Investigator during the following periods: 16-week Treatment Period, 12-week Maintenance Period, 4-week Titration/Stabilization Period, and 3-week Taper Period
- Number of and reason for subjects requiring premature tapering due to TEAEs
- Number of and reason for subjects requiring a dose reduction during the Stabilization Period due to TEAEs
- Incidence of treatment-emergent SAEs during the following periods: 16-week Treatment Period, 12-week Maintenance Period, 4-week Titration/Stabilization Period
- Changes in clinical laboratory test parameters (including hematology, blood chemistry, and urinalysis)
- Changes in vital sign parameters (including pulse rate, SBP, DBP, and respiratory rate)
- Changes in 12-lead ECG parameters
- Physical examination (including body weight) and neurological examination findings
- Changes in Psychiatric and Mental Status exam
- Occurrence of valvular abnormalities or pericardial effusion changes or other significant abnormalities as identified by 2-dimensional Doppler echocardiogram at each assessment by central reader
- Changes in withdrawal symptoms using Clinical Institute Withdrawal Assessment-Benzodiazepines (CIWA-B) from the end of the 16-week Treatment Period (Visit 7) to the end of the Taper Period (Visit 8) and the end of the SFU Period (Visit 9 [30 days after the last IMP intake])

## **4.3 Other variables**

### **4.3.1 Pharmacokinetic variables**

Blood concentrations of PSL will be determined from samples obtained in the study during the Treatment Period in order to investigate the following variable:

- The population PK profiles of PSL

Blood concentrations of concomitantly administered AEDs will also be evaluated for evidence of DDIs with PSL at steady state.

Comparison may be made between blood concentration data of PSL and [REDACTED] metabolite derived from the volumetric absorptive microsampling MITRA® technology.

Additionally, evaluation of PSL and [REDACTED] metabolite in plasma may be undertaken from trough samples. The collection of plasma samples for this comparison may cease during the course of the study based on periodic review of the data.

## 5 STUDY DESIGN

### 5.1 Study description

EP0092 is a multicenter, randomized, double-blind, placebo-controlled, parallel-group study in adults ( $\geq 18$  years of age) with drug-resistant epilepsy who continue to have uncontrolled focal-onset seizures despite treatment with at least 4 prior AEDs, including current AEDs. All eligible subjects will have an epilepsy diagnosis and at least 4 observable focal-onset seizures per 28 days despite treatment with at least 1 to 3 AEDs, with or without neurostimulation devices at stable regimens, with doses and settings individually optimized for efficacy and safety/tolerability.

Subjects should be educated to complete their diary entries accurately as per instruction.

The study is composed of 4 periods (see [Figure 5-1](#) for a schematic diagram):

#### Baseline Period (4 weeks)

During the Screening Visit (Visit 1, Week -4), subjects will sign an ICF prior to the conduct of any study-related procedure or pretreatment assessments, and the subject's eligibility will be determined on the basis of the inclusion/exclusion criteria. Subject eligibility related to seizure frequency will be evaluated based on Investigator assessment of the subject report on historical seizure count during the 8 weeks prior to the Screening Visit (Visit 1) for the retrospective seizure baseline. Eligible subjects will be given a diary and receive instructions to further document seizures during the 4-week Baseline Period for a prospective seizure baseline. All subjects must have been on a stable dose of their current AEDs during the 8 weeks prior to the Screening Visit (Visit 1). For the neurostimulation device (if applicable), the settings should be stable for 12 weeks prior to the Screening Visit (Visit 1). Both should be stable throughout the study until the end of the Treatment Period. The Investigator will be asked to send documentation of a video-electroencephalogram (EEG) report, as per instruction, to the UCB Study Physician or representative for confirmation of eligibility before randomization of the subject.

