##### **13.3.1.1 Analysis of the primary efficacy variable for the US FDA, PMDA, Chinese FDA, and other regulatory authorities not specified in Section 4.1.1.2**

Pairwise comparisons of 400mg bid, 200mg bid, and 100mg bid dose groups versus placebo will be carried out using the following analysis model. Type 1 error will be controlled by the Hochberg step-up procedure within SAS® Proc Multtest.

For the US FDA, PMDA, Chinese FDA, and other regulatory authorities not specified in Section 4.1.1.2, the primary efficacy variable is the change in log-transformed observable focal-onset seizure frequency from Baseline, over the 12-week Maintenance Period. The 28-day Baseline and post-Baseline (maintenance) seizure frequency will be transformed with the natural logarithm, specifically  $\ln(x+1)$ , where x represents the 28-day seizure frequency. The transformed seizure frequency data will be analyzed using analysis of covariance (ANCOVA)

with treatment group as the main factor, Baseline log-adjusted seizure frequency as a continuous covariate, and Baseline SV2A and region used as a categorical factors. Pairwise contrasts will be constructed to compute estimated effects of each dose from placebo.

All pairwise analyses of the primary efficacy variable will be repeated on the PPS.

If the second analysis is performed for Chinese FDA (Section 13.3.1), a dose will be concluded statistically significant in the second analysis only if the dose is statistically significant in the first and second analyses.

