### **13.8 Determination of sample size**

In the event that 2 data analyses are conducted to accommodate an extended enrollment period in China, the initial data cut and analysis will be performed after all randomized non-Chinese subjects (approximately 400) have completed or terminated the study. The safety and efficacy analyses from this first data cut will serve as the basis for the European, North American, and Japanese submissions for marketing authorization. The power for this analysis is greater than 90%, at the 2-sided 5% significance level. Because of uncertainty regarding the time point when China will join the global program and the duration of recruitment in China, a second efficacy and safety analysis for all randomized subjects (approximately 500) will also be performed: the power in this case remains greater than 90%, at the 2-sided 5% significance level. The safety and efficacy analyses from the second data cut will serve as the basis for submission for marketing authorization only for China.

The sample size was calculated based on achieving 90% power to observe a statistically significant result for either the 400mg bid and 200mg bid or 200mg bid and 100mg bid doses when compared to PBO for both the primary variable for FDA/PMDA/CFDA, change from Baseline of the log transformed ( $\ln x+1$ ) 28-day adjusted seizure frequency, and the primary variable for EMA, the 75% responder rate. The log reduction from Baseline in seizure frequency

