was assumed to be 0.195 for PBO and 0.670, 0.754, and 0.780 for 100mg bid, 200mg bid, and 400mg bid doses of PSL, respectively. A common SD of 0.985 was assumed. For the 75% responder rate endpoint, assumptions were a 0.121 responder rate for PBO and corresponding responder rates of 0.301, 0.332, and 0.342 for the 100mg bid, 200mg bid, and 400mg bid doses of PSL, respectively. These estimates are based on prior experience in epilepsy together with the EP0069 study results. A significance level of 0.05 was chosen, and a 2-sided test assumed. With power of greater than 90%, a 2-sided Type-1 error of 5%, and all dose groups of the same size, 100 subjects are required per arm, giving a total of 400 subjects. An additional group of approximately 100 subjects will be included from China. Assuming a screening failure rate of approximately 20%, it is anticipated to enroll approximately 625 subjects (approximately 500 in Europe, North America, and Japan, and approximately 125 in China) and randomize approximately 500 subjects (approximately 400 in Europe, North America, and Japan, and approximately 100 in China) in the study.

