3.3 Definition of Baseline values

3.3.1 Baseline for variables based on seizure count

Baseline values for seizure frequency variables will be derived from diary data recorded by the subject during the 4-week Baseline Period. This diary is collected at the Baseline Visit (Visit 2, Day 1). The Baseline value will be the seizure frequency per 28 days during the Baseline Period and is defined as the number of seizures standardized to a 28-day baseline period. It is computed for each subject as the number of seizures recorded over the subject's baseline diary period, divided by the subject's total number of non-missing days in that period, multiplied by 28. See details for calculation of seizure frequency in Section 8.1.1.1.

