4.1 Adjustments for covariates

The primary and selected efficacy analyses will be adjusted for baseline log-transformed seizure frequency and for the stratification factors:

- Current use of AEDs with binding to SV2A proteins (LEV and/or brivaracetam): Yes or No
- Geographical Region: Investigative sites have been identified in the following regions and countries at the time of this SAP amendment. More regions and/or countries may be identified and will be included in the analyses in accordance to the randomization strata:
 - Europe (Australia, Austria, Belgium, Bosnia and Herzegovina, Bulgaria, Croatia, Czech Republic, Denmark, Estonia, Finland, France, Germany, Greece, Hungary, Ireland, Italy, Netherlands, Norway, Poland, Portugal, Romania, Serbia, Slovakia, Spain, Sweden, Switzerland, Turkey, and United Kingdom)
 - North America (Canada, Mexico, and United States)
 - Japan

To ensure at least 5 subjects in each region in the FAS at each treatment group, Japan will be pooled with North America to form a non-Europe region for the efficacy analyses.

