6.3.3.6 Historical seizure count and cluster count

The Historical Seizure Count and Historical Cluster Count CRF records the number of seizures and clusters experienced by the subject during the past 2 months prior to the Screening Visit. The number of seizures and clusters will be summarized by seizure type and month.

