The primary efficacy available for the EMA is the 75% responder rate over the 12-week Maintenance Period. Analyses of the primary variable for the EMA submission will be done on the FAS as described below.

The analysis of 75% responder rate will be based on a logistic regression model with factors for treatment group (PSL 400mg bid, 200mg bid, 100mg bid and placebo), Region (Europe or Non-Europe), Baseline SV2A use (Yes or No) and log-transformed Baseline seizure frequency as a continuous covariate. If there are issues with convergence, covariates will be dropped sequentially in the order of Region, and then Baseline SV2A use (Yes or No) if further needed. Odds Ratios of PSL dose to placebo will be obtained and tested for difference from unity (2-sided) for the dose groups 400mg bid, 200mg bid, and 100mg bid. The evaluation of statistical significance will be based on the Hochberg procedure as described in Section 4.5. Both multiplicity adjusted p-values and unadjusted p-value will be presented.

If there is <2 responders in a treatment group, results will also be provided for an exact conditional logistic regression model where treatment group is included in the model and Region (Europe or non-Europe) and Baseline SV2A use (Yes or No) are included as strata.

8.1.2.4 Supportive and sensitivity analyses for the primary variable for submission to the EMA and regulatory authorities who reference EMA

Due to early termination of the study and COVID-19 global pandemic, all sensitivity analyses will not be executed.

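### The 8-week historical seizure count is collected before randomisation but is in neither primary model; adding it beside the 4-week diary Baseline would give a modest, nearly free gain in precision

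*Protocol*

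**What the plan says.** Two seizure baselines exist before randomisation. Protocol 5.1 (Baseline Period) describes an investigator-assessed subject report, the "historical seizure count during the 8 weeks prior to the Screening Visit (Visit 1) for the retrospective seizure baseline", and then a diary kept for the following 4 weeks. Inclusion criterion 6 and Protocol 9.1 use both for eligibility: an average of at least 4 observable focal-onset seizures per 28 days with at least 1 in each 4-week interval of the history, and at least 4 in the Baseline Period.

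After eligibility, the historical count is only described. SAP 6.3.3.6 says: "The number of seizures and clusters will be summarized by seizure type and month". SAP 6.3.3 also lists the epilepsy history.

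The analysis baseline is the diary alone (SAP 3.3.1): "Baseline values for seizure frequency variables will be derived from diary data recorded by the subject during the 4-week Baseline Period". SAP 4.1 then states: "The primary and selected efficacy analyses will be adjusted for baseline log-transformed seizure frequency and for the stratification factors". The ANCOVA in Protocol 13.3.1.1 is specified "with treatment group as the main factor, Baseline log-adjusted seizure frequency as a continuous covariate", with SV2A use and region as further factors. The EMA logistic model in SAP 8.1.2.3 carries "log-transformed Baseline seizure frequency as a continuous covariate", again with SV2A use and region. Neither document says why the historical count is left out.

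**The concern.** A covariate measured before randomisation that predicts the outcome reduces residual variance and does not bias the randomised comparison. The historical count is a natural candidate. It covers twice the time of the diary Baseline, on the same background regimen, because Protocol 5.1 requires stable AED doses over those 8 weeks. It also helps to show whose Baseline month was unusually high or low. A single month's count that must reach 4 for entry will be atypical for some subjects.

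What is at stake is the width of the confidence intervals and some power in the log-frequency analysis. Validity is not in question.

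**Working it through.** **Inputs.** From Protocol 13.8: log reductions of 0.195 (placebo) and 0.670, 0.754 and 0.780 (100, 200 and 400mg bid), so differences of 0.475, 0.559 and 0.585; SD 0.985; 100 per arm; 75% responder rates of 0.121 against 0.301, 0.332 and 0.342. On the error rate: "A significance level of 0.05 was chosen, and a 2-sided test assumed". The success criterion is "achieving 90% power to observe a statistically significant result for either the 400mg bid and 200mg bid or 200mg bid and 100mg bid doses", on both primary variables. From Protocol 13.3.1.1 and SAP 4.5: Hochberg over three doses.

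**Step 1: the plan's own figure.** For one contrast, power = Φ(δ / (σ√(2/n)) − 1.96). For 100mg: 0.475 / (0.985 × √0.02) = 0.475 / 0.1393 = 3.41, and Φ(1.45) = 92.6%. The 200mg and 400mg contrasts give 98.0% and 98.7%. For the responder rate the three contrasts give 88.3%, 95.1% and 96.5%. Simulating four arms with a shared placebo group and Hochberg, the stated criterion is met in 96.7% of trials for log change and 92.9% for responders. Success on both is 0.967 × 0.929 = 89.8% if the endpoints were independent, and up to 92.9% if they are positively correlated. This agrees with the claim of more than 90%, so the sample size contains no error on which this point depends.

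**Step 2: how much variance the covariate could remove.** If r is the partial correlation of the log historical count with the outcome, given the log diary Baseline, residual variance is multiplied by 1 − r². The documents do not give r, so it was obtained by simulation on assumed inputs: monthly Poisson counts with lognormal rates, month-to-month variation within subjects, individual response variation, and both entry thresholds applied. Recall error in the history is a log-scale SD.

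| Assumed recall-error SD | Setting A: fall in treatment-effect variance | Setting B: fall in residual variance |
|---|---|---|
| 0 | 10% | 11.9–12.4% |
| 0.3 | 8% | 9.4–10.3% |
| 0.6 | 4% | 5.7–6.3% |
| 1.0 | 2% | about 3% |

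Setting A: log-rate SD 0.9 around ln 9 per 28 days, monthly SD 0.5, response SD 0.85, giving an SD of change near 0.95. Setting B: log-rate SD 1.0 around ln 8, monthly SD 0.5–0.6, response SD 0.8, giving an SD of change of 0.92–0.98 and 12–13% placebo responders. Allowing for variation in these inputs, a fair range is about 1% to 13%. Settings with an SD of change of only 0.69–0.80 gave 4–17%, but they do not match the plan's 0.985 and are set aside.

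**Step 3: what this means for power** at 100 per arm, taking 0.985 as the residual SD before the new covariate, so that the new SD is 0.985 × √(1 − cut):

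| Variance cut | SD | 100mg pairwise power | Plan's criterion, log change |
|---|---|---|---|
| 0 | 0.985 | 92.6% | 96.7% |
| 1% | 0.980 | 92.9% | 96.8% |
| 4% | 0.965 | 93.6% | 97.3% |
| 9% | 0.940 | 94.7% | 98.0% |
| 13% | 0.919 | 95.5% | 98.4% |

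Equivalent sample size per arm is 100 / (1 − cut), so 101 to 115.

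**Step 4: the responder model.** In Setting A, with 3,000 simulated trials of 100mg against placebo for each recall-error value, logistic power started at 87–88% and rose by 0.8, 1.6, 0.5 and 0.2 points for recall error 0, 0.3, 0.6 and 1.0. The simulation standard error of each power estimate is about √(0.88 × 0.12 / 3000) = 0.6 points, so the gain is barely distinguishable from none.

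**The case against.** The strongest reply is that adjusting for the outcome's own prospective Baseline and the stratification factors is coherent and standard, and that the design meets its power target without more. That stands, and it limits this point to a suggestion about efficiency.

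Several stronger readings are tempting, and the documents do not support them:

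- **That the 4-week count is the noisier of the two.** Eight weeks carries less sampling error, but that count is recalled, while the 4-week count is a daily diary reviewed by the investigator. In Setting A the diary Baseline correlated 0.46 with the outcome. The history correlated 0.52 with perfect recall, but 0.40 at recall-error SD 0.6. The case is for adding the history, not for replacing the diary.
- **That selection discredits only the diary count.** The historical count is an entry threshold too.
- **That the models adjust for nothing but the 4-week count.** SV2A use and region are also included.
- **That the size of the loss is known.** Matching the plan's SD and placebo responder rate does not identify r. Protocol 13.8 also does not say whether 0.985 is the SD of raw change or a residual SD. If it is raw change, the diary covariate already removes about 7–10% of variance in Setting B, so 100mg power starts nearer 94–95% and there is less left to gain.
- **That the covariate would remove chance 75% responders after a high Baseline month.** The endpoint and its 4-week Baseline would be unchanged, so those responders would remain.

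**Conclusion.** The omission is real: an informative pre-randomisation measurement, already collected, enters neither primary model, and no reason is given. It is a missed efficiency, not an error, a bias or a power shortfall.

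Under the assumptions above, the ANCOVA residual variance would fall by roughly 1–13%. Pairwise power for 100mg at 100 per arm would rise by between a fraction of a point and about 3 points. On the plan's criterion for log change the rise is under 2 points from about 97%. The responder rate is the limiting endpoint for joint success, and there the gain is negligible. Every matching setting tried showed some ANCOVA gain, even with poor recall, but its size depends on recall error and month-to-month variation that the documents do not report. The study ended early, so precision may matter more than at the planned size; the documents do not give the final numbers per arm.

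**What to change.** Before unblinding, amend SAP 4.1 and 8.1.2.1, and 8.1.2.3 for consistency, and record the change in SAP 3.9:

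- **Add** a second continuous covariate, ln(x+1), where x is the historical IA1+IB+IC frequency per 28 days: the 8-week total divided by 2, with clusters counted as episodes as in SAP 8.1.1.1. SAP 6.3.3.6 refers to the past 2 months, so confirm that the CRF's two months are the protocol's two 4-week intervals.
- **Keep** the log 4-week diary Baseline, SV2A use and region in the models. Endpoint definitions and the 4-week Baseline for change and percent reduction stay as they are.
- **Missing history:** use a simple rule that draws on no treatment information, such as imputing the overall mean, so that no subject leaves the FAS analysis.
- **Non-convergence:** drop this covariate first, ahead of region and SV2A use. Leave the exact conditional logistic model unchanged.

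The cost is one degree of freedom and minor programming; no new data are needed. If the data are already unblinded, leave the primary models alone and report this as a labelled supportive analysis.
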